4.8 Removal of Subjects from Study Treatment and/or Study as a Whole

Patients can be taken off the study treatment and/or study as a whole at any time at their own request, or they may be withdrawn at the discretion of the investigator for safety, behavioral or administrative reasons. The reason(s) for discontinuation must be clearly documented on the appropriate eCRF and may include:

- Patient voluntarily withdraws from treatment (follow-up permitted)
- Patient withdraws consent (no follow-up permitted)
- Patient is unable to comply with protocol requirements (follow-up permitted)
- Patient demonstrates disease progression (per parameters above, follow-up permitted)
- Patient experiences unacceptable toxicity
- Treating physician determines that continuation on the study would not be in the patient's best interest
- Patient becomes pregnant
- Patient develops a second malignancy that requires treatment which would interfere with this study
- Patient becomes lost to follow-up (LTF)

4.9 Patient Replacement

Any patient who signs consent but does not receive study treatment may be replaced.

5.0 STUDY PROCEDURES

Day of each cycle	Screening ¹	On Treatment (1 cycle = 12 weeks) ^{12,13}																		Off Treatment		
		Cycle 1 (±3 days)							Cycle 2 (±3 days)							Cycle 3+ (±3 days)						
		1	15	29	43	57	71	1	15	29	43	57	71	1	15	29	43	57	71	End of Treatment ¹⁴	Follow -Up ¹⁵	
Weeks on study		1	3	5	7	9	11	13	15	17	19	21	23	25	27	29	31	33	35 +			
Assessment or Activity																						
Informed Consent	X																					
Medical history	X																					
Physical exam ²	X	X	X	X	X	X	X	X	X	X	X	X	X	X	X	X	X	X	X	X	X	
ECOG status	X	X	X	X	X	X	X	X	X	X	X	X	X	X	X	X	X	X	X	X	X	
ConMeds	X	X	X	X	X	X	X	X	X	X	X	X	X	X	X	X	X	X	X	X	X	
Adverse events	X	X	X	X	X	X	X	X	X	X	X	X	X	X	X	X	X	X	X	X	X ¹⁵	
Scans ³	X	X ³						X ³								X ³					X	
Lesion Photos ¹⁶	X	X						X								X					X	
CBC with diff ⁴	X	X	X	X	X	X	X	X	X	X	X	X	X	X	X	X	X	X	X	X	X	
Chemistry panel ⁵	X	X	X	X	X	X	X	X	X	X	X	X	X	X	X	X	X	X	X	X	X	
Amylase/Lipase	X	X ⁶						X ⁶								X ⁶					X	
TSH (free T4) ⁷	X	X ⁷						X ⁷								X ⁷						
Pregnancy test ⁸	X	X						X								X					X	
Nivolumab ⁹		T	T	T	T	T	T	T	T	F	F	F	F	F	F	F	F	F				
Ipilimumab ¹⁰		X		X		X		X		X		X		X		X		X				
Tissue collection ¹¹	X	X ¹¹																				
Survival status																					X	

T = 240mg nivolumab

F = 480mg nivolumab

¹ CBC with diff and Chemistry panel should be within 14 days of registration; all other screening procedures should take place within 28 days of registration unless specified otherwise.

² Includes vital signs (pulse, blood pressure), height and smoking history (baseline only) and weight.

³ Imaging must include Chest, Abdomen, and Pelvis as well as a bone scan. Scans may be by CT, PET/CT or MRI (per treating investigator's discretion) with contrast unless strictly contraindicated as well as a bone scan; the same modality used at baseline should be used

throughout. Tumor assessment should be done at screening, cycle 2 day 1 (\pm 1 week) and Day 1 of each cycle (every 12 weeks) thereafter, regardless of dosing schedule until progression or treatment discontinuation whichever occurs later. Tumor assessments will incorporate both RECIST and clinical criteria. Brain MRI is the preferred imaging method for evaluating CNS metastasis, and assessment is only required during screening for eligible subjects with symptomatic CNS involvement.

If PD is confirmed at any time, see section 4.4 on how to determine whether patient can be considered for further treatment. If patient continues, scans should be obtained every 12 weeks until PD is confirmed by 2 consecutive scans.

⁴ CBC with differential will include WBC, ANC, ALC, Platelets, and Hemoglobin. It will be collected within 14 days of registration, every 14 days during cycles 1 & 2, and prior to each treatment thereafter (day 1, 29, 43, and 57 of each cycle).

⁵ Chemistry panel will include glucose, calcium, albumin, ALT, AST, sodium, potassium, total bilirubin, alk phos, and creatinine. It will be collected within 14 days of registration, every 14 days during cycles 1 & 2, and prior to each treatment thereafter (day 1, 29, 43, and 57 of each cycle).

⁶ Amylase and lipase will be assessed at screening and Day 1 of each cycle.

⁷ TSH will be tested at screening and Day 1 of each cycle. If TSH is abnormal, free T4 should be tested

⁸ Serum or urine test for females of child-bearing potential (FOCBP) within 72 hours of registration. FOCBP are also required to have a negative pregnancy test within 24 hours of starting nivolumab and Day 1 of each cycle.

⁹ Nivolumab will be administered IV at 240mg over 30 minutes every two weeks in combination with ipilimumab as follows:
Cycle 1, C2D1, & C2D15: 240mg over 30 minutes (-5 / +15 minutes) every 14 days.

Starting with Cycle 2 Day 29: 480mg over 60 minutes (-10 / +15 minutes) every 28 days until PD, intolerance, or withdrawal of consent.

¹⁰ Ipilimumab will be administered IV at 1mg/kg over 90 minutes every six weeks in combination with nivolumab. Dosing will be based on body weight measured every 6 weeks, prior to each ipilimumab infusion. Nivolumab will be given before ipilimumab.

¹¹ Archival tissue (or fresh tissue if not available) will be collected at baseline for all patients. If the patient agrees, additional tissue may be collected during biopsies performed as standard of care during study participation. Please see separate lab manual for details.

¹² Treatment will start within 14 days of registration, and continue until confirmed disease progression, unacceptable toxicity, or withdrawal of consent.

¹³ Study procedures may take place within 24 hours prior to study treatment.

¹⁴ End of Treatment visit will occur 30 days (\pm 7 days) after stopping nivolumab or combination treatment, or before the patient starts new treatment, whichever occurs first. Adverse events will be recorded for up to 12 weeks after stopping treatment.

¹⁵ Patients will be followed and assessed for adverse events every 4 weeks (\pm 7 days) by routine clinic visit for the first 12 weeks after treatment. Thereafter, patients will be followed (either by routine clinic visit or by phone) every 3 months for up to 2 years while off treatment to document survival and disease progression.

¹⁶ Photographs for disease assessments will be taken by study staff on a study-supplied digital camera. It is preferred that these photos be taken on a white background (wall of patient room) using a ruler measurement when possible. Photographs should not include any identifying characteristics

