4.4 Treatment with ipilimumab and or nivolumab beyond progression

In the event of an initial assessment of PD (based on RECIST Version 1.1), a subject may continue to receive the assigned study treatment as long as none of the criteria listed below are met. Criteria for discontinuation of investigational product include:

1. Confirmed PD: An initial assessment of PD by RECIST Version 1.1 will be confirmed by a repeat evaluation at the next tumor assessment time point, but no sooner than 4 weeks later (see Section 4.3.1 for disease evaluation).
2. Meets any of the other investigational product discontinuation criteria (Section 4.1.6)
3. Clinical symptoms or signs indicating significant PD such as the benefit-risk ratio of continuing therapy is no longer justified.
4. Decline in ECOG performance status.
5. Threat to vital organs/critical anatomical sites (eg, spinal cord compression) requiring urgent alternative medical intervention, and continuation of study therapy would prevent institution of such intervention.

If the lesions included in the tumor burden subsequently regress to the extent that the criteria for PD are no longer met, then treatment may continue according to the treatment schedule.

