6.6.3 Evaluation of best overall response

The best overall response is the best response recorded from the start of the treatment until disease progression/recurrence (taking as reference for progressive disease the smallest measurements recorded since the treatment started). The patient's best response assignment will depend on the achievement of both measurement and confirmation criteria. Responses will be assessed using CT scans or magnetic resonance imaging according to standard RECIST 1.1 criteria in order to assess disease progression. These criteria will also allow for patients who experience an initial disease flare, and as some patients who will have a delayed response may experience an initial disease flare, we will allow patients to continue receiving nivolumab beyond progression (see section 4.4).

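### The passages on treatment after progression use confirmed PD both as the entry to further treatment and as its end, and section 4.4, to which they defer, has two faulty references

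*Combined protocol and SAP*

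**What the plan says.** Section 4.4 sets the rule after a first RECIST 1.1 assessment of PD: "a subject may continue to receive the assigned study treatment as long as none of the criteria listed below are met". Confirmed PD is the first criterion on that list, and the section defines it this way: "An initial assessment of PD by RECIST Version 1.1 will be confirmed by a repeat evaluation at the next tumor assessment time point". It sets a minimum gap of 4 weeks before the repeat and, on how disease is evaluated, sends the reader to section 4.3.1. The second criterion is "Meets any of the other investigational product discontinuation criteria (Section 4.1.6").

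In section 5.0, footnote 12 has treatment run until progression is confirmed, in line with 4.4. Footnote 3 says: "If PD is confirmed at any time, see section 4.4 on how to determine whether patient can be considered for further treatment". It adds that, for a patient who continues, "scans should be obtained every 12 weeks until PD is confirmed by 2 consecutive scans".

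Sections 4.2.1 (nivolumab) and 4.2.2 (ipilimumab) and footnote 9 (nivolumab 480 mg) end dosing at progression, without the word confirmed and without a pointer to 4.4. Sections 4.1 and 4.6 do point to 4.4 for patients who continue after progression.

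Section 6.6.3, on best overall response, says "we will allow patients to continue receiving nivolumab beyond progression (see section 4.4"). It does not mention ipilimumab. The heading of 4.4 names both drugs.

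**The concern.** These passages decide when two drugs with immune-related toxicity are stopped in patients whose aggressive disease is progressing. Different staff consult different pages: the schedule footnotes, the dosing sections, or 4.4. If those pages use the same word for opposite purposes, or leave out the exception that another page supplies, post-progression exposure can vary between patients for reasons unrelated to their condition. In a single-arm trial of 29 patients with descriptive safety reporting, a few such patients would make the toxicity summary harder to interpret.

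**Working it through.** No planned figure is in dispute, so the main check sets the passages side by side.

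**1. Trigger and drugs**

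| Place | At first PD | At confirmed PD | Drugs |
|---|---|---|---|
| 4.4 | may continue | discontinuation criterion | assigned treatment; heading names both |
| 5.0, footnote 12 | continues, by implication | treatment ends | not specified |
| 5.0, footnote 3 | not addressed | go to 4.4 to see if further treatment is possible; confirmation is also the end of repeat scanning | not specified |
| 4.2.1 and footnote 9 | dosing ends | not addressed | nivolumab |
| 4.2.2 | dosing ends | not addressed | ipilimumab |
| 4.1, 4.6 | see 4.4 | see 4.4 | study treatment |
| 6.6.3 | may continue, see 4.4 | not addressed | nivolumab named |

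Taken literally, footnote 3 sends a patient with confirmed PD to a section whose first criterion stops that patient. Two adjacent sentences of the footnote use confirmation first as the entry to continuation and then as the end of scanning.

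**2. What confirms PD**

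Scheduled scans are 12 weeks apart (4.1; 5.0 footnote 3; 6.1). If first PD is on the scan at week t, the next is at t + 12. Since 12 ≥ 4, section 4.4 is met. The scans at t and t + 12 are two in a row, so footnote 3 is met as well if the first PD scan counts. The rules can part in two ways:
- an unscheduled repeat at 4 to under 12 weeks is accepted under 4.4;
- footnote 3 is taken to mean two further scans, which gives 2 × 12 = 24 weeks.

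The text states neither. Footnote 3 simply does not say whether the first PD scan is one of the two. This comparison uses the 12-week interval; section 6.2 gives 8 weeks, which is a separate inconsistency.

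**3. Exposure that depends on the wording**

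Take first PD on the C2D1 scan and confirmation at C3D1, with no dose delays. From 4.2.1, 4.2.2 and footnotes 9 and 10, the infusions from C2D1 up to but not including C3D1 are:
- nivolumab on days 1, 15, 29 and 57: 4 infusions;
- ipilimumab on days 1 and 43: 2 infusions.

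Under 4.4 up to 4 and 2 may be given. Under 4.2.1 and 4.2.2 read alone, none would be given once PD is declared. If the day 1 infusions precede the scan reading, 3 and 1 are at issue.

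**4. References in 4.4**

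Section 4.1 has no subsection 4.1.6; the permanent discontinuation criteria are in 4.3.2. Section 4.3.1 covers dose delays; disease evaluation is in section 6 and in footnote 3 of section 5.0.

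**5. Effect on the PFS decision rule**

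Inputs from 10.2: 15 patients, continue if at least 8 are progression-free at 3 months; reject the null if at least 11 of 29 are progression-free at 6 months. Under exponential PFS, (S3, S6) = (0.50, 0.25) under the null and (0.7071, 0.50) under the alternative.

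- P(stop early) = P[Bin(15, S3) ≤ 7] = 50.0% (null), 4.37% (alternative).
- P(reject) = Σ over k = 8 to 15 of P[Bin(15, S3) = k] × Σ over j = 0 to k of P[Bin(k, S6/S3) = j] × P[Bin(14, S6) ≥ 11 − j] = 7.01% (null), 90.1% (alternative).

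These reproduce the plan's 50%, 4.4%, 7% and 90%. No term depends on treatment given after progression.

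**The case against.** The strongest answer is that 4.4 controls. Sections 4.1, 4.6 and 6.6.3 and footnote 3 all refer to it, and footnote 12 agrees with it. A reader who follows the references reaches one result. The second sentence of footnote 3 also suggests that its first use of *confirmed* was meant as first documented.

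Much of this stands, and it rules out several stronger readings that a reader might infer:
- **That the plan lays down two rival rules, so that one patient must be stopped under one section and treated under another.** Footnote 3 refers the question to 4.4 and grants nothing itself. Conflicting action follows only if a passage is read without its reference, or if the passage has none.
- **That 6.6.3 permits nivolumab only, giving 4 nivolumab and 0 ipilimumab infusions in the example above.** The sentence does not exclude ipilimumab, and it cites 4.4.
- **That confirmation takes 24 weeks.** This is one possible reading of footnote 3, not a stated rule.
- **That best-response data would mix regimens.** Section 6.6.3 counts best response only up to progression.

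The answer does not dispose of the point. The benign reading of footnote 3 replaces the word it uses. Sections 4.2.1 and 4.2.2 and footnote 9 carry no pointer to 4.4. And 4.4, on which the answer relies, has two references that fail.

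**Conclusion.** The concern holds as an inconsistency of wording in operative stopping rules. The clearest conflict is over confirmed PD: footnote 3 against 4.4 and footnote 12. The unqualified stopping rules in 4.2.1, 4.2.2 and footnote 9, and the two faulty references in 4.4, are also real. The drug wording in 6.6.3 and the two-scan wording in footnote 3 are ambiguities, not contradictions.

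In the worked case the size is up to 4 nivolumab and 2 ipilimumab infusions over one 12-week interval. That assumes PD on a scheduled scan, confirmation at the next one, no dose delays, and a reader who uses the dosing sections without the exception in 4.1 and 4.6.

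The PFS decision rule and its operating characteristics are unaffected, taking the PFS event at the first documented RECIST 1.1 progression or death.

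**What to change.** Reconcile 4.4, footnotes 3, 9 and 12 of section 5.0, and sections 4.2.1, 4.2.2 and 6.6.3, so that together they give:
- one trigger for considering treatment after progression, and one consequence of confirmed PD;
- one definition of confirmation, stating whether the first PD scan counts and whether an unscheduled repeat does;
- one statement of which drugs may continue.

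In 4.4, replace the reference to 4.1.6 with the section that holds the permanent discontinuation criteria (4.3.2), and the reference to 4.3.1 with the place that describes disease evaluation. The clinical team must decide which treatment wording stands; this review takes no position on it.

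The cost is amendment text only. Sample size, decision rule and operating characteristics stay as they are, and no new scheduled assessment is needed if the existing scans are used for confirmation.

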2.0 OBJECTIVES & ENDPOINTS

2.1 Primary Objective & Endpoint

To determine progression free survival (PFS) in patients with newly recurrent HER2 negative IBC treated with nivolumab and ipilimumab according to Response Evaluation Criteria in Solid Tumors (RECIST) v 1.1.⁴⁶

The time in months from start of treatment to progression or death will be measured for all patients who receive at least one dose of study drug. Patients will be followed up to 2 years after completion of treatment.

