4.7 Duration of Follow Up

All patients will be followed for adverse events for 12 weeks after last dose of nivolumab and or ipilimumab, or until the patient starts a new treatment, whichever occurs first. Patients who discontinue treatment for unacceptable adverse event(s) will be followed until resolution or stabilization of the adverse event (i.e. the grade is not changing). If a patient stops treatment due to unacceptable adverse event(s) but has not demonstrated

NU Study Number: NU 16B07
Other Study Number: CA 209-782

disease progression, then the patient will be followed with imaging studies every 8 weeks until the time of progression radiographically according to RECIST 1.1 criteria. In the event that a radiographic response is detected, then this event will be included as a response in the final analysis, and the time of progression used in calculation of the survival analysis. Patients will be followed for survival status every 3 months for 2 years after treatment discontinuation or until death, whichever occurs first.

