6.0 ENDPOINT ASSESSMENT

6.1 Definitions

For the purposes of this study, patients should be re-evaluated for response every 12 weeks (± 1 week). In addition to a baseline scan, confirmatory scans should also be obtained 8 weeks following initial documentation of objective response greater than Stable Disease (SD). Tumor assessments for all subjects should continue as per protocol even if dosing is interrupted. Tumor measurements should be made by the same investigator or radiologist for each assessment whenever possible. Changes in tumor measurements and tumor responses to guide ongoing study treatment decisions will be assessed by the investigator using RECIST.

Response and progression will be evaluated in this study using the new international criteria proposed by the revised Response Evaluation Criteria in Solid Tumors (RECIST) guideline (version 1.1)⁴⁶. Changes in the largest diameter (unidimensional measurement) of the tumor lesions and the shortest diameter in the case of malignant lymph nodes are used in the RECIST criteria.

High resolution CT with oral/intravenous contrast or contrast-enhanced MRI is the preferred imaging modalities for assessing radiographic tumor response. If a subject has a known allergy to contrast material, please use local prophylaxis standards to obtain the assessment with contrast if at all possible, or use the alternate modality. In cases where contrast is strictly contraindicated, a non-contrast scan will suffice. Screening assessments should be performed within 28 days of registration. Brain MRI is the preferred imaging method for evaluating CNS metastasis, and assessment is required during screening in all eligible subjects. All known or suspected sites of disease (including CNS if history of CNS metastases) should be assessed at screening and at subsequent assessments using the same imaging method and technique. If more than one method is used at screening, then the most accurate method according to RECIST 1.1 should be used when recording data, and should again be used for all subsequent assessments. Previously treated CNS metastases are not considered measurable lesions for purposes of RECIST determined response. Subjects with a history of brain metastasis should have surveillance MRI approximately every 12 weeks, or sooner if clinically indicated.

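### Footnote 3, section 4.7 and footnote 15 give conflicting off-treatment assessment rules for PFS, and section 10.2 does not say how a patient with no 6-month tumor assessment is counted

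*Combined protocol and SAP*

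**What the plan says.** The primary endpoint is PFS "according to Response Evaluation Criteria in Solid Tumors (RECIST) v 1.1" (section 2.1; section 6.2 agrees). Four places bear on how it is ascertained once treatment stops.

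- **Section 5.0, footnote 3.** Tumor assessments fall on Day 1 of each 12-week cycle, "regardless of dosing schedule until progression or treatment discontinuation whichever occurs later". The reason for stopping is not a condition.
- **Section 4.7.** If a patient stops for unacceptable adverse events without progression, "then the patient will be followed with imaging studies every 8 weeks until the time of progression radiographically according to RECIST 1.1 criteria". For other patients the section gives only survival status every 3 months.
- **Section 5.0, footnote 15.** Adverse events are assessed every 4 weeks "by routine clinic visit for the first 12 weeks after treatment. Thereafter, patients will be followed" at a visit "or by phone) every 3 months for up to 2 years while off treatment to document survival and disease progression".
- **Section 6.1.** "Tumor assessments for all subjects should continue as per protocol even if dosing is interrupted". This covers interruption and does not name permanent discontinuation.

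Sections 4.6 and 4.8 list ways off treatment that involve neither progression nor toxicity: intercurrent illness, inability to comply, physician decision, and "Patient voluntarily withdraws from treatment (follow-up permitted").

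Section 10.2 continues past stage 1 if at least 8 of 15 are progression-free at 3 months and rejects the null if at least 11 of 29 are progression-free at 6 months. It does not say what establishes that status, and neither it nor section 10.3 gives a rule for a missing assessment.

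**The concern.** RECIST progression needs a measured increase in target lesions, a new lesion or unequivocal non-target progression (section 6.6). A phone call shows none of these, yet footnote 15 names it as a way to document progression.

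A site that works from section 4.7 and footnote 15 finds no instruction to image a patient who stops by choice. A site that works from footnote 3 finds that imaging continues to progression. The primary endpoint could therefore be measured differently according to why the patient stopped and which text the site follows.

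The trial has no control arm and its decision rests on a count. Whoever finalizes the 11/29 tally must place each unassessed patient on one side or the other. One choice raises the type I error and the other lowers power, and the plan leaves it open.

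**Working it through.** **Passages side by side, for a patient off treatment without progression**

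| Text | Stopped for toxicity | Stopped for another reason |
|---|---|---|
| Footnote 3 | 12-weekly assessment to progression | same |
| Section 4.7 | 8-weekly imaging to progression | survival status only |
| Footnote 15 | adverse-event visits for 12 weeks, then visit or phone every 3 months | same |

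The toxicity column disagrees on the interval. The other column disagrees on whether there is any imaging.

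**Timing.** Phone contact may begin only 12 weeks after treatment ends, so it cannot supply a 3-month count. Six months is about week 26, and 26 − 12 = 14, so phone contact can fall at the 6-month landmark only for patients who stop before about week 14. For those who stop later but before the 6-month assessment, the gap is the absence of an imaging instruction in section 4.7 and footnote 15, not the phone call.

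**Reproducing the stated design (section 10.2).** Inputs: 3-month PFS p3 = 0.50 (null) or 0.7071 (alternative); 6-month PFS p6 = 0.25 or 0.50; cohorts of 15 and 14.

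- Stage 1: X ~ Bin(15, p3); continue if X ≥ 8.
- First cohort at 6 months: Y1 given X ~ Bin(X, p6/p3).
- Second cohort: Y2 ~ Bin(14, p6).
- Reject the null if Y1 + Y2 ≥ 11.

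Exact enumeration gives early stopping of 50.0% (null) and 4.37% (alternative), type I error 7.01% and power 90.13%. The plan states 50%, 4.4%, 7% and 90%, so its figures reproduce.

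**Sensitivity to scoring.** Let k of the 14 second-cohort patients have no 6-month assessment. The documents do not give k; 1 to 3 is my assumption.

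- A, carried forward from a progression-free 3-month scan: under the null, Y2 = Bin(14 − k, 0.25) + Bin(k, 0.50).
- B, scored progression-free whatever the true state: under the null, Y2 = Bin(14 − k, 0.25) + k.
- C, scored as failures: under the alternative, Y2 = Bin(14 − k, 0.50).

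| k | A: type I error | B: type I error | C: power |
|---|---|---|---|
| 0 | 7.0% | 7.0% | 90.1% |
| 1 | 8.3% | 10.9% | 88.0% |
| 2 | 9.8% | 16.1% | 85.3% |
| 3 | 11.3% | 22.5% | 81.7% |

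B is an upper bound. It credits even patients who have died, although death is a PFS event and survival is tracked. A is the more realistic case because it keeps the 3-month scan result.

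**Cross-check over both cohorts.** Suppose an assumed 10% of all patients go unscanned between months 3 and 6. Carry-forward replaces the null p6 by 0.25 + 0.10 × (0.50 − 0.25) = 0.275 and gives type I error 11.7%. Scoring them as failures replaces the alternative p6 by 0.50 × 0.90 = 0.45 and gives power 80.7%.

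**The case against.** The strongest reply is that footnote 3 already settles the matter. It keeps any patient without progression on 12-weekly assessments whatever the reason for stopping, and footnote 15 can be read as governing only how status is recorded. Section 10.2 also calls for a 6-month evaluation in both cohorts, and the schedule's scan row carries an off-treatment mark, although its column cannot be determined from the text available.

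Much of this stands. A reader might infer that the protocol replaces scans with phone calls once treatment stops. It does not: footnote 15 nowhere ends the footnote 3 assessments.

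A reader might also infer that unassessed patients are scored progression-free, or that Kaplan-Meier PFS is therefore too long. No passage says so. Section 6.7 makes PFS evaluability depend on a post-baseline scan (section 6.2 requires only one dose), and censoring at the last assessment, if used, would not credit unobserved time. Nor can phone contact distort the 3-month count, given its 12-week delay.

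The reply does not remove the conflict. Section 4.7 singles out adverse-event stoppers for imaging, which would be unnecessary if footnote 3 were understood to cover everyone, and its interval differs. The 6-month evaluation in section 10.2 is not defined as a tumor assessment. Section 6.7 does not help with a patient scanned once and not again.

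**Conclusion.** The point holds as an inconsistency between passages plus a missing counting rule. Footnote 3, section 4.7 and footnote 15 cannot all be followed as written, and under the latter two a patient who stops without progression for a non-toxicity reason before the 6-month assessment may have no tumor assessment at that landmark. The documents do not support the stronger claim that such patients are counted as successes.

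The size is illustrative. For 1 to 3 second-cohort patients, carry-forward moves type I error from 7.0% to between 8.3% and 11.3%, and the upper bound is 10.9% to 22.5%. Counting the same patients as failures moves power from 90.1% to between 88.0% and 81.7%. These figures rest on the assumed number of patients and on the plan's exponential PFS rates. The correction is worth making because a few patients matter at an 11/29 threshold and the change is mainly one of wording.

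**What to change.** 1. Reconcile footnote 3, section 4.7 and footnote 15 so that every patient off treatment without progression, whatever the reason, stays on one stated tumor-assessment schedule until progression. The study team must settle the interval, since the passages give both 8 and 12 weeks.
2. Limit phone contact in footnote 15 to survival status and new therapy.
3. State in section 10.2 that progression-free status at 3 and 6 months requires a tumor assessment, with an allowed window, and state how a patient without one is counted. This rule is needed in any case, because section 4.8 permits no follow-up after consent is withdrawn.

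For patients who stop for reasons other than toxicity, this adds no assessments beyond those footnote 3 already requires. The cost is that some patients who have left treatment must still attend scans. If missing assessments are counted as failures, the power loss shown above is a real price and should be acknowledged when the rule is chosen. Results under the opposite scoring can be reported as a sensitivity analysis.
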